2.3. Data Handling

2.3.1. Measurement Times

2.3.1.1. Visit Windows

Visit windows will not be used. The visit time point entered on the case report forms will be used. Unscheduled assessments, if any, will be listed, but will not be included in tabulations by visit.

2.3.1.2. Baseline Values

The screening assessments are performed within 28 days of Cycle 1, Day 1, before the first dose of study medication. Unless otherwise mentioned, baseline will be the last observation before patients receive initially assigned dose. Generally, this will be Cycle 1 Day 1 pre-dose measurements. If a pre-dose assessment is not performed on Cycle 1 Day 1, the immediate previous non-missing value, including screening, will be treated as baseline. If there are multiple baseline assessments, the most recent one will be flagged as the baseline value and will be used for statistical analysis (evaluations may occur on the same day as Study Day 1, prior to dosing).

2.3.2. Missing Data Conventions

Unless otherwise specified, missing data will be considered missing and will not be imputed.

2.3.3. Imputation of Incomplete Dates

Imputation of partial dates may be performed during the data analysis and will be documented. For start date of AE or Concomitant Medication (CM) with a missing day, the imputed date is the first day of the month. For stop date of AE or CM with a missing day, the imputed date is the last day of the month. For start date with both missing day and missing month, the imputed date is the patient start study date if AE or CM start year is the same as study start year. Otherwise, the imputed start date is the first day of the year. For stop date with both missing day and missing month, the imputed date is the patient end of study date if AE or CM stop year is the same as the study end year. Otherwise, the imputed stop date is the last day of the year.

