8.5 Supportive Care Guidelines

- Medications may be administered for the management of symptoms associated with the administration of FF-10502-01, as required.
- Adequate treatment for nausea and/or vomiting and diarrhea is permitted at the discretion of the Investigator.
- Infusion reactions were reported at the RP2D of 90 mg/m²; pre-treatment with corticosteroids or other medications may be given at the Investigator's discretion.
- Granulocyte stimulating growth factors (eg, G-CSF or GM-CSF) are not allowed during Cycle 1 except for the following situations: Grade 4 neutropenia lasting ≥ 7 days, failure of \geq Grade 3 ANC to recover to Grade 1 within 4 weeks, or febrile neutropenia (defined as ANC $< 1000/\text{mm}^3$ with a single temperature of $> 38.3^\circ\text{C}$ or sustained temperature of $\geq 38^\circ\text{C}$ for over one hour). After Cycle 1, use of granulocyte growth factors are allowed for prophylaxis or management of neutropenia.
- Erythropoiesis-stimulating agents, transfusions, etc, are permitted for management of hematologic toxicities.

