10.1.4 Adverse Event Reporting Period

The adverse event reporting period begins from the date of the first dose of study drug to 28 days following the last dose of study drug.

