10.1.5 Recording of Adverse Events

Each AE should be recorded in standard medical terminology on the AE CRF module. Whenever possible, the AE should be evaluated and reported as a diagnosis rather than as individual signs or symptoms. For example, cough, runny nose, sneezing, sore throat, and head congestion should be reported as 'upper respiratory infection'. If a definitive diagnosis is not possible, the individual signs and symptoms should be recorded. Dates of start (onset) and stop (recovery), action taken, and outcome will be recorded in the AE CRF module.

All clinically significant abnormal changes in laboratory parameters will be recorded as an AE on the AE module, with the following exceptions: clinically significant abnormal laboratory changes determined to be related to the study condition and concomitant conditions, eg, diabetes, of which the investigator was previously aware and that have not worsened.

The investigator will evaluate all AEs with regard to maximum intensity and relationship to study drug, as follows.

10.1.5.1 *Maximum Intensity*

Maximum intensity should be assigned using one of the severity grades as outlined in the National Cancer Institute Common Terminology Criteria for Adverse Events (NCI CTCAE v4.03); if the AE is not specifically listed in CTCAE v4.03, use the following grades:

- Grade 1: mild
- Grade 2: moderate
- Grade 3: severe
- Grade 4: life-threatening
- Grade 5: death

10.1.5.2 *Relationship to Study Drug*

The degree of certainty with which an AE is attributed to study drug (or alternative causes, eg, natural history of the underlying diseases, concomitant therapy, etc) will be determined by how well the event can be understood in terms of known pharmacology of the study drug and/or

reactions of similar nature previously observed with study drug. Each AE will be assigned one of the following five categories:

- Not related: There is not a temporal relationship to the study drug (eg, too early, too late), or there is a reasonable causal relationship to another drug, concurrent illness, or circumstance.
- Unlikely related: There is a temporal relationship to study drug, but there is not a reasonable causal relationship between the time of study drug administration and the AE (ie, it is doubtful the AE is related to the study drug); could be reasonably explained by other factors, including underlying disease, complications, concomitant drugs, or concurrent treatment.

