3.4.2. Adverse Events

AEs reported from the date of the first dose of study drug to 28 days following the last dose of study drug will be presented. All AEs will be coded based on the Medical Dictionary for Regulatory Affairs (MedDRA; Version 17.0 or higher). An AE will be considered a treatment emergent adverse event (TEAE) if the onset is after the first dose of study drug or if the condition was present at baseline but worsened after the first dose.

All AEs for each patient will be listed, including intensity grading, relationship to study drug, action taken and outcome. Table summaries and patient listings of deaths, serious TEAEs, and TEAEs leading to treatment discontinuation will be provided.

TEAE summaries will be presented for patients in Phase 1 dose escalation phase and for patients in Phase 2a expansion phase by disease cohort. All TEAE summaries will show the number and percentage of patients experiencing at least 1 TEAE for each preferred term, arranged by system organ class, and the number of unique occurrences of the event. Separate summaries will be produced by relationship to study medication, and by severity, and for those events with an incidence of at least 2% in any group or overall. Patients with multiple events will be counted only once per SOC and preferred term. For each level of summarization, the event with the highest level of severity, or strongest drug relationship will be presented. TEAEs with Grade 3 or Grade 4 and drug-related TEAEs with Grade 3 or Grade 4 will be summarized. TEAEs leading to study drug interruption or discontinuation, Grade 3 and 4 TEAEs, Serious TEAEs will be summarized and also provided in a separate listing. In addition, a summary of TEAEs for the total occurrences of the events will be provided.

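### AE start dates with a missing day are imputed to the first of the month with no floor at first dose, so such events in the first-dose month fail the TEAE definition

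*SAP*

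**What the plan says.** **Imputation (SAP 2.3.3).** The rule for a missing day is: "For start date of AE or Concomitant Medication (CM) with a missing day, the imputed date is the first day of the month". When day and month are both missing, "the imputed date is the patient start study date if AE or CM start year is the same as study start year"; otherwise the first day of the year is used. The section does not say whether the patient's start study date means consent, screening or first dose. It opens permissively: "Imputation of partial dates may be performed during the data analysis and will be documented".

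**TEAE definition (SAP 3.4.2).** An AE is treatment-emergent "if the onset is after the first dose of study drug or if the condition was present at baseline but worsened after the first dose". Protocol 11.3.1.1 has the same lower bound and adds an upper limit of 28 days after the last dose. Neither document says how to classify an AE whose timing is uncertain.

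**AE period.** Protocol 10.1.4: "The adverse event reporting period begins from the date of the first dose of study drug". The opening sentence of SAP 3.4.2 also presents AEs starting with that date. Both therefore include the day of first dose.

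**The concern.** The first of a month can never be later than a first dose given in that month. Applied literally, the imputation gives every missing-day AE from that month an onset on or before first dose, and the TEAE definition then rejects it. The worsening clause does not rescue a new event.

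This conflicts with the plan's own AE period: events are collected only from first dose, so an imputed onset before first dose falls outside the collection window. The rule is also uneven. When day and month are both missing there is a floor of a kind, the start study date. When the month is known there is none, so the better-documented event can receive the earlier date.

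The safety profile is part of the primary objective, and the AE tables listed in SAP 4.1.6.2 are TEAE tables. The error runs in one direction, removing early events. Groups are small: SAP 2.1 plans 1 to 6 patients per dose cohort and up to 10 in Cohort 12, where one patient is 1/10, or 10 percentage points, of an incidence.

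**Working it through.** The documents give no figure on this point, so there is none to reproduce. The check applies the date rules to every possible case.

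**Inputs**
- Imputed start when the day is missing: first of the onset month (SAP 2.3.3).
- TEAE test: onset after first dose (SAP 3.4.2, Protocol 11.3.1.1), applied to dates as imputed > first dose. The variant imputed ≥ first dose is shown for comparison.
- Window: the 28 days of Cycle 1 in Cohorts 1 to 12.
- Assumptions: first-dose dates uniform over four calendar years (1,461 dates) and true onset uniform over the 28 days.

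**Step 1: onset days that fall in the first-dose month.** For first dose on day d of a month of length L, the number is min(28, L − d + 1). Summed over d, this is 406 + 28 × (L − 28), which gives 406, 434, 462 and 490 for months of 28, 29, 30 and 31 days. Four years contain 3, 1, 16 and 28 such months:

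3 × 406 + 1 × 434 + 16 × 462 + 28 × 490 = 22,764

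All combinations: 1,461 × 28 = 40,908. Share in the first-dose month: 22,764 / 40,908 = **55.6%**.

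**Step 2: strict after.** The imputed date is never later than first dose, so all 22,764 fail. That is **100%** of missing-day AEs in the first-dose month and 55.6% of missing-day Cycle 1 AEs.

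**Step 3: on or after, imputation unchanged.** Only patients dosed on the first of a month pass: 48 months × 28 days = 1,344. Failures: 22,764 − 1,344 = 21,420, which is 21,420 / 22,764 = **94.1%** of those in the first-dose month and 21,420 / 40,908 = 52.4% of missing-day Cycle 1 AEs.

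**Step 4: effect on all Cycle 1 AEs.** The share lacking a start day is not given, so a range is assumed. Loss = share × 0.556.

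| Assumed share with missing day | Cycle 1 AEs lost from TEAE tables |
|---|---|
| 1% | 0.6% |
| 2% | 1.1% |
| 5% | 2.8% |
| 10% | 5.6% |

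**Step 5: which change is needed.**

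| Rule | Missing-day Cycle 1 AEs lost |
|---|---|
| As written, strict after | 55.6% |
| On or after, imputation unchanged | 52.4% |
| Floor at first dose, strict after kept | 55.6% |
| Floor at first dose and on or after | 0% |

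On a date comparison, neither change is sufficient alone.

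**Day and month both missing, year of study start.** If the start study date is the first-dose date, the event fails strict after and passes on or after. If it is an earlier date, the event fails both.

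**The case against.** **Same-day events.** A reader might infer that every AE on the day of first dose, including infusion reactions, drops out. The documents do not support that. Onset after the first dose orders two events; it need not mean AE date > first-dose date, and no such comparison is specified. Protocol 10.1.5 says: "Dates of start (onset) and stop (recovery), action taken, and outcome will be recorded in the AE CRF module". It does not say that only dates are recorded, and the CRF is not among the documents. Protocol 8.5 notes that "Infusion reactions were reported at the RP2D", but not that they occurred at the first infusion; reactions at later infusions pass the test. What stands is that the wording leaves a reaction starting during the first infusion unclear.

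**Start study date.** A reader might take this as a date up to 28 days before dosing, since screening may be that early. The term is undefined, and SAP 2.3.1.2 uses Study Day 1 for the dosing day, which favours a first-dose reading. The point is the missing definition.

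**Reach.** It would be too strong to say that all AE output, or the dose-finding result, depends on the TEAE flag. SAP 3.4.6 summarises discontinuations due to AEs and death without it, SAP 4.3 lists DLTs and deaths separately, and nothing links DLT, MTD or RP2D decisions to it.

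**A tempting figure.** With dosing days even over a 30-day month, 29/30 = 97% of first-dose days are not the first. That is not the share of affected AEs, because patients dosed on the first contribute more in-month onset days. The shares are those in steps 2 and 3.

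**Mitigation.** Imputation is optional and documented, monitoring covers AE documentation and source data verification, and a pre-dose onset would look anomalous. SAP 3.4.2 also promises a listing of all AEs. These reduce the harm but do not remove it. Without imputation, a partial date in the first-dose month cannot be shown to be after first dose and no default applies; and the main AE listing named in SAP 4.3 is headed as TEAEs.

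**Conclusion.** The concern holds for new AEs with a missing start day and onset in the first-dose month. All of them fail the definition under strict after, and about 94% would still fail under on or after. They make up about 56% of missing-day Cycle 1 AEs, given uniform first-dose dates and onset days over a 28-day cycle. The loss as a share of all Cycle 1 AEs, about 0.6% to 5.6%, rests on the assumed 1% to 10% rate of missing days. The number is probably small in a closely monitored Cycle 1, but the stated rule misclassifies in a known direction and should be corrected before analysis. Fully dated events on the day of first dose are lost only if after is programmed as a strict date comparison; for them the wording needs clarification. Dose-finding decisions are not affected.

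**What to change.** 1. **SAP 2.3.3, AE start dates.** When the known part of the onset date is compatible with the month (day missing) or year (day and month missing) of first dose, impute the first-dose date, unless the stop date shows that the event ended earlier. Otherwise keep the first of the month or year. For AEs, replace the undefined start study date with the first-dose date.
2. **SAP 3.4.2 and Protocol 11.3.1.1.** Define TEAE onset as on or after the date of first dose, keeping the worsening clause. This makes the floored dates count and matches the AE period in Protocol 10.1.4 and the opening of SAP 3.4.2. Change both documents so that their definitions stay aligned.

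The cost is a few sentences and a small program change. TEAE counts may rise slightly.

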2.4. Statistical Methods

2.4.1. General Overview and Plan of Analysis

All data will be analyzed using Statistical Analysis System (SAS Version 9.4 or higher for Windows, SAS Institute, Cary, NC). Continuous variables will be summarized using number, mean, standard deviation, median, minimum, and maximum. Categorical variables will be summarized using frequencies and percentages.

2.4.2. Hypothesis Testing

No formal hypothesis tests are planned.

2.4.3. Modeling

Not Applicable in this study.

2.4.4. Multiplicity Issues/Multiple Comparisons

There is no planned Multiplicity Issues/Multiple Comparisons analysis for this study.

2.4.6. Interim Analysis

No formal interim analysis is planned. AE listings and appropriate summary tables will be generated for Scientific Review Committee meetings and Development Safety Update Reports (DSURs).

2.4.7. Pharmacokinetic and Pharmacodynamic Analyses

Pharmacokinetic and Pharmacodynamic data will be summarized in a separate report.

3. Statistical Analysis

Data will be presented for clinical review and interpretation. Categorical variables will be summarized using frequency counts and percentages. Continuous variables will be summarized using descriptive statistics (n, mean, SD, median, minimum, and maximum). All listings will be presented for the safety analysis population except for PK and PD data.

3.1. Enrollment and Disposition of Patients

Patients with advanced solid tumors will be included.

Major selection criteria are: age ≥ 18 years, histologically confirmed solid tumor with documented disease progression following previous therapy. Patients must be ≥ 4 weeks beyond chemotherapy (or ≥ 5 half-lives for targeted agents, whichever is shorter), radiotherapy, major surgery, or other experimental treatments, and recovered from all acute toxicities (\leq Grade 1), have adequate renal and hepatic function, and no known history of significant cardiac disease.

The analyses of patient disposition will be performed on the safety analysis population for patients in Phase 1 dose escalation and for patients in Phase 2a expansion phase by disease cohort treated at MTD. The number of patients screened, treated, completed study, and terminated early from the study, along with their reasons for early termination, will be presented.

3.2. Baseline Characteristics

3.2.1. Demographic

Summary statistics for demographic characteristics will be presented for patients in Phase 1 dose escalation phase and for patients in Phase 2a expansion phase by disease cohort treated at MTD using the safety analysis population. Tabulations will be performed for age, sex

(male or female), ethnicity (Hispanic/Latino or other), and race (American Indian or Alaska Native, Black or African American, White, Asian, Native Hawaiian or Other Pacific Islander, Unknown, or other). Age will be calculated as the number of complete years between a patient's date of birth and the date of screening visit.

3.2.2. Physical Characteristics

Summary statistics will be presented for height (cm) and weight (kg) at screening for patients in dose escalation phase and for patients in expansion phase by disease cohort treated at MTD using the safety analysis population. ECOG performance status at screening will be summarized.

3.2.3. Disease Characteristics

Summary statistics will be presented for primary diagnosis at screening for patients in Phase 1 dose escalation phase and for patients in Phase 2a expansion phase by disease cohort treated at MTD using the safety analysis population. Tabulations will be presented for primary tumor type, primary tumor location, sites of extension/metastases, and stage of disease. Medical history findings will be listed but not summarized.

3.2.4. Concomitant Medications at Entry

Concomitant medications coded using WHO Drug Dictionary will be listed but not summarized for patients in Phase 1 dose escalation phase and for patients in Phase 2a expansion phase. Medication start and stop dates will be compared to the date of first dose of medication to allow medications to be classified as either prior or concomitant. Medications that start and stop prior to the date of first dose of study medication will be classified as prior medications. If a medication starts before the date of first dose of study medication or starts on or after the first dose of study medication, and stops on or after the date of first dose of study medication, then the medication will be classified as a concomitant medication.

3.3. Analysis of Efficacy

All efficacy analyses will be conducted for patients in Phase 1 dose escalation phase and for patients in Phase 2a expansion phase by disease cohort treated at MTD using the FAS population.

3.3.1. Primary Endpoints

The primary efficacy endpoint is the proportion of patients in each disease cohort (cholangiocarcinoma, gallbladder carcinoma, urothelial carcinoma, or other solid tumor) with objective response (OR) within 4 cycles of study drug. Thus, this is the proportion of patients in Cohorts 1-12 with an OR within 16 weeks of their first dose of study drug and the proportion of patients in Cohort 13 with an OR within 12 weeks of their first dose of study drug. The OR rate is defined as the proportion of patients with a confirmed complete or partial response. Ninety percent confidence intervals for the OR rate will be estimated. See Appendix A for the schedule of study procedures.

Target Lesions in patients with measurable disease is evaluated by the PI as follows:

- **Complete Response (CR):** Disappearance of all target lesions. Any pathological lymph nodes (whether target or non-target) must have reduction in short axis to < 10mm.
- **Partial Response (PR):** At least a 30% decrease in the sum of the diameters of target lesions, taking as reference the baseline sum diameters.
- **Progressive Disease (PD):** At least a 20% increase in the sum of the diameters of target lesions, taking as reference the smallest sum on study (this includes the baseline sum if that is the smallest on study). In addition to the relative increase of 20%, the sum must also demonstrate an absolute increase of at least 5 mm. (Note: the appearance of one or more new lesions is also considered progression).
- **Stable Disease (SD):** Neither sufficient decrease to qualify for PR nor sufficient increase to qualify for PD, taking as reference the smallest sum diameters while on study.
- **Not Evaluable:** One or more Target Lesions could not be assessed.

Non-Target Lesions (for all other lesions, or in patients with non-measurable disease only) is evaluated by the PI as follows:

- **Complete Response (CR):** Disappearance of all non-target lesions and normalization of tumor marker level. All lymph nodes must be non-pathological in size (< 10 mm short axis).
- **Non-CR/Non-PD:** Persistence of one or more non-target lesion(s) and/or maintenance of tumor marker level above the normal limits.
- **Progressive Disease (PD):** Unequivocal progression of existing non-target lesions, or appearance of one or more new lesions. When the patient also has measurable disease, to achieve 'unequivocal progression' on the basis of non-target disease, there must be an overall level of substantial worsening in non-target disease such that, even in the presence of SD or PR in target disease, the overall tumor burden has increased sufficiently to merit discontinuation of therapy.
- **Not Evaluable:** One or more Non-Target Lesions could not be assessed.

Overall Response

At each protocol-specified time point (Day 28 of every 2nd cycle for Cohorts 1-12; and day 21 of every 2nd cycle for Cohort 13), an overall response assessment is made by the PI. Criteria for overall response for target and non-target disease are summarized in the table below:

Overall Response for Target and Non-Target Disease

	Target Lesion	Non-Target Lesion	New Lesions
Complete Response (CR)	CR	CR or NA	No
Partial Response (PR)	CR	Non-CR/Non-PD	No
	CR	Not evaluated	No
	PR	Non-PD or not all evaluated	No
Stable Disease (SD)	SD	Non-PD or not all evaluated	No
Progressive Disease (PD)	PD	Any	Yes or No
	Any	PD	Yes or No
	Any	Any	Yes
Not Evaluable (NE)	Not all evaluated	Non-PD	No

Best Overall Response

The Best Overall Response is the best response across all protocol time points.

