9.2.2 Requirements During Treatment Cycles After Cycle 1 (Cycles 2, 3, 4, etc)

9.2.2.1 Day 1 of Each Cycle (± 2 days)

- Abbreviated physical examination
- Vital signs
- ECOG Performance Status
- Weight
- The following lab tests (within 3 days of each cycle – see [Table 3](#) for a list of lab tests):

- Hematology. Note: In addition to total lymphocyte counts, T cell (CD4 and CD8) and B cell counts will be obtained.
- Serum chemistry
- Urinalysis
- Review of concomitant medications
- Assessment of AEs
- Administration of FF-10502-01 over a 1-hour period

9.2.2.2 *Day 8 of Each Cycle (±2 days)*

- The following lab tests (see [Table 3](#) for a list of lab tests):
 - Hematology
- Review of concomitant medications
- Assessment of AEs
- Administration of FF-10502-01 over a 1-hour period

9.2.2.3 *Day 15 of Each Cycle (±2 days) [Cohorts 1 to 12 only]*

- The following lab tests (see [Table 3](#) for a list of lab tests):
 - Hematology
- Review of concomitant medications
- Assessment of AEs
- Administration of FF-10502-01 over a 1-hour period

9.2.2.4 *End of Cycle 2 and Every 2 Cycles Thereafter (±3 days)*

- Disease-specific assessment (CT, MRI scans)
- Review of concomitant medications
- Assessment of AEs

9.3 **At Relapse or Progression of Disease**

- Disease-specific assessment (CT, MRI scans)
- Review of concomitant medications
- Assessment of AEs

9.4 **End of Treatment (28 days, ± 5 days, from the last dose of Study Drug)**

- Physical examination
- Vital signs
- ECOG Performance Status
- Weight
- The following lab tests: (See [Table 3](#) for a list of lab tests)

- Hematology. Note: In addition to total lymphocyte counts, T (CD4 and CD8) and B cell counts will be obtained at end of treatment.
- Serum chemistry
- Urinalysis
- 12-lead ECG
- Review of concomitant medications
- Assessment of AEs

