PD	Any	Yes or No	PD
Any	PD	Yes or No	PD
Any	Any	Yes	PD

CR = complete response, PR = partial response, SD = stable disease, PD = progressive disease, NE = not evaluable

Table 5. Criteria for Overall Response for Non-target Disease Only

Non-Target Lesions	New Lesions	Overall Response
CR	No	CR
Non-CR/non-PD	No	Non-CR/non-PD
Not all evaluated	No	NE
Unequivocal PD	Yes or No	PD
Any	Yes	PD

CR = complete response, PR = partial response, SD = stable disease, PD = progressive disease, NE = not evaluable

- **Evaluation of Best Overall Response**

The best overall response is the best response recorded across all time points. If CR or PR is recorded, confirmation should be sought 28 days later. When SD is believed to be the best response, no confirmation is required.

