10.2.4 Timing of Assessments to Determine Response

Disease assessments will be made at the end of Cycle 2 and every two cycles thereafter. Disease assessments may be made at other time points at the discretion of the Investigator.

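### The 28-day confirmation scan is missing from both schedules and from the SAP's response time points, so some responses the protocol would confirm may be counted as non-responses

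*SAP*

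**What the plan says.** **Confirmation.** Protocol 10.2.2.1, on best overall response: "If CR or PR is recorded, confirmation should be sought 28 days later". The same paragraph takes the best response over all time points, without restricting them to scheduled visits.

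**Schedule.** Protocol 10.2.4: "Disease assessments will be made at the end of Cycle 2 and every two cycles thereafter". Section 9.2.2.4 agrees and gives a window of ±3 days. Tables 6 and 7 in Appendix D show disease assessments at screening, at the end of Cycle 2 and every two cycles after that, and at progression or relapse. Neither table has a 28-day confirmation assessment. Section 10.2.4 does add: "Disease assessments may be made at other time points at the discretion of the Investigator".

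**Endpoint.** SAP 3.3.1: "The OR rate is defined as the proportion of patients with a confirmed complete or partial response". Protocol 11.3.2.1 also defines a confirmed rate. Both documents count responses within 16 weeks (Cohorts 1 to 12) or 12 weeks (Cohort 13).

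**SAP derivation.** SAP 3.3.1 places the overall response assessment as follows: "At each protocol-specified time point (Day 28 of every 2nd cycle for Cohorts 1-12; and day 21 of every 2nd cycle for Cohort 13"). It then says: "The Best Overall Response is the best response across all protocol time points". It states no confirmation interval and does not say which scans can confirm. On off-schedule data, SAP 2.3.1.1 says: "Unscheduled assessments, if any, will be listed, but will not be included in tabulations by visit".

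**The concern.** The endpoint depends on confirmation, but the confirming scan is not in the schedule, and the SAP does not say whether such a scan counts. Its wording on time points is narrower than the protocol's.

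Take a Cohort 11 patient with PR at Week 8, PR on a Week 12 confirmation scan, and PD at Week 16. Under protocol 10.2.2.1 this is a confirmed PR. An analyst who uses only the SAP's listed time points sees PR followed by PD and scores an unconfirmed response. A patient with the same course at a site that kept strictly to Table 6 has no Week 12 scan, so the response cannot be confirmed at all. Two reasonable analysts, or two sites with different habits, could therefore classify the same disease course differently on the primary efficacy endpoint. The Cohort 11 and 13 decision rules turn on small counts (6 of 50 and 4 of 27), so a few such patients matter.

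**Working it through.** **1. Calendar, for a response first seen on the first scheduled scan**

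| | First scan | 28-day confirmation | Next scheduled scan | Gap on schedule |
|---|---|---|---|---|
| Cohorts 1 to 12 | Week 8 | Week 12 | Week 16 | 8 weeks |
| Cohort 13 | Week 6 | Week 10 | Week 12 | 6 weeks |

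The patients at risk are those whose response holds at 4 weeks but ends before 8 weeks (Cohort 11) or 6 weeks (Cohort 13). A response first seen at Week 16 (12) is confirmed after the window under either interval, so it is not part of this loss. On schedule, the confirming scan also sits exactly at the end of the window, and one taken 3 days late falls just outside it.

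**2. The plan's own power, reproduced**

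Inputs are from protocol 11.1. Cohort 11: n1 = 25, stop at 1 or fewer responses, n = 50, reject at 6 or more, p0 = 5%, p1 = 16%. Cohort 13: n1 = 15, stop at 0, n = 27, reject at 4 or more, p0 = 5%, p1 = 20%.

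With r1 the stopping count and c the rejection count:

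P(reject | p) = Σ over x from r1+1 to n1 of Bin(x; n1, p) × P[Bin(n − n1, p) ≥ c − x]

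- Cohort 11: alpha 0.035, power 0.807.
- Cohort 13: alpha 0.043, power 0.810.

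Both agree with the stated 80% power and 5% one-sided error. If the futility rule is treated as non-binding, power is 0.832 and 0.818.

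**3. Effect if only scheduled scans can confirm**

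Assumptions not in the documents:

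- Response duration from first documentation is exponential with median m months.
- Every response starts at the first scan.
- No 28-day scan is done and used.
- p1 is the rate of response confirmed at 28 days.

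Among responses that hold at 28 days, the share lost is L = 1 − 2^(−g/m). Here g is the extra wait in months: 4 weeks / 4.345 = 0.921 in Cohort 11 and 2 weeks / 4.345 = 0.460 in Cohort 13. For example, Cohort 11 with m = 3 gives L = 1 − 2^(−0.307) = 0.192, and the effective rate is 16% × (1 − 0.192) = 12.9%. Power is the step 2 formula at p1 × (1 − L).

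| Median (months) | Cohort 11: L | Rate | Power | Cohort 13: L | Rate | Power |
|---|---|---|---|---|---|---|
| 3 | 19.2% | 12.9% | 0.61 | 10.1% | 18.0% | 0.73 |
| 6 | 10.1% | 14.4% | 0.72 | 5.2% | 19.0% | 0.77 |
| 9 | 6.8% | 14.9% | 0.75 | 3.5% | 19.3% | 0.79 |

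**4. A milder case**

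If half of the at-risk responses are lost and futility is non-binding, power at medians of 3, 5 and 9 months is 0.75, 0.78 and 0.81 in Cohort 11, and 0.78, 0.80 and 0.81 in Cohort 13.

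**The case against.** A reader might infer that confirmation necessarily takes 8 (6) weeks under this plan and that responses will be lost. The documents do not support that.

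- Protocol 10.2.4 permits scans at other times, and 10.2.2.1 asks for this one. A scan the protocol asks for can fairly be read as a protocol time point.
- SAP 2.3.1.1 keeps unscheduled assessments out of by-visit tables only. The OR proportion within 4 cycles is not a by-visit table.
- SAP 3.3.1 says when the investigator makes an overall response assessment. It does not say that other assessments are ignored.
- The only confirmation rule in either document is the protocol's. The SAP's confirmed OR rate, read with it, gives a confirmed PR in the Week 8, 12, 16 example.

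The direction is not fixed for every output either. The SAP's best overall response sentence has no confirmation requirement, so read alone it would count the example patient as PR. It would over-count responses rather than lose them.

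A reader might also infer that the decision counts were set on a rate confirmed at 28 days. Protocol 11.1 speaks only of response by RECIST 1.1. The link to confirmation comes from the endpoint definition in 11.3.2.1 and is an inference.

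These points stand, and they make the loss conditional. They do not remove the gap. Permission to scan is not a schedule, no text says that off-schedule scans count towards response, and the SAP's listed time points suggest otherwise. For the confirmed OR rate, the schedule-only reading can only remove responses confirmed at 28 days.

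**Conclusion.** The concern holds in conditional form. The protocol's confirmation rule, its visit schedule and the SAP's response time points do not agree, and the SAP leaves the interval and the eligible scans for its confirmed rate undefined. If sites follow the schedule, or the analyst counts only the SAP's time points, first-scan responses that hold at 28 days but progress before the next scheduled scan may be scored as non-responses.

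The power figures of 0.61 to 0.75 (Cohort 11) and 0.73 to 0.79 (Cohort 13) are worst-case values for assumed medians of 3 to 9 months. They also rest on binding futility, although protocol 11.1 says only that enrollment may be suspended and that prolonged stable disease is considered first. The loss shrinks if some responses begin later or if some 28-day scans are done and used. In the milder case, power is within about 2 points of 80% or above it, except in Cohort 11 at a 3-month median. The figures show that the ambiguity can matter; they do not forecast the trial's power. The change should be made because it settles the primary efficacy count at little cost.

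**What to change.** In SAP 3.3.1:

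- Derive overall response at every disease assessment, scheduled or unscheduled, and define best overall response over all disease assessments instead of protocol time points.
- State that a CR or PR is confirmed by any later assessment showing CR or PR, at the protocol's 28-day interval (with the existing ±3-day scan window) or later, with no intervening PD.
- State whether the confirming scan must itself fall inside the 16 (12)-week window, or only the first response must.

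In protocol Appendix D, reconcile Tables 6 and 7 with 10.2.2.1 by a footnote for the confirmation assessment.

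The cost is SAP wording and a footnote. No procedure is added beyond what 10.2.2.1 already requests. The small downside is that unscheduled scans must be included in the response derivation.
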